- 3.1.2.7 Uncontrolled intercurrent illness which would interfere with the ability of the patient to carry out the treatment program, including, but not limited to, active second malignancy other than a cancer that has been successfully treated resulting in a high likelihood of long-term survival (e.g. completely resected basal cell or squamous cell carcinoma of the skin, stage 1 renal cell carcinoma treated with partial nephrectomy, treated low risk prostate cancer, etc.), inflammatory bowel disease (e.g. Crohn's disease or ulcerative colitis), active diverticulitis, ongoing or active infection, symptomatic congestive heart failure, unstable angina pectoris, cardiac arrhythmia, or psychiatric illness/social situations that would limit compliance with study requirements.
- 3.1.2.8 Pregnant women are excluded from this study because the vaccines used in the study

may have the potential for teratogenic or abortifacient effects. Because there is an unknown but potential risk for adverse events in nursing infants secondary to treatment of the mother with the vaccine, breastfeeding should be discontinued if the mother is treated with vaccines. These potential risks may also apply to other agents used in this study. Patients must agree to use adequate contraception (hormonal or barrier method of birth control; abstinence) prior to study entry and for the duration of study participation. Should a woman become pregnant or suspect she is pregnant while her partner is participating in this study, she should inform her treating physician immediately

- 3.1.2.9 Concurrent use of systemic steroids, except for physiologic doses of systemic steroids for replacement or local (topical, nasal, or inhaled) steroid use. Limited doses of systemic steroids to prevent IV contrast, allergic reaction, or anaphylaxis (in patients who have known contrast allergies) are allowed. Although topical steroids are allowed, steroid eye-drops are contraindicated
- 3.1.2.10 Altered immune function, including immunodeficiency or history of immunodeficiency; eczema; history of eczema, or other eczematoid skin disorders; or those with acute, chronic or exfoliative skin conditions (e.g. atopic dermatitis, burns, impetigo, varicella zoster, severe acne, or other open rashes or wounds). There is an increased risk to patients or contacts with eczema, atopic dermatitis, and other immune deficiencies who are at risk for eczema vaccination.

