- 3.1.2.11 Medical conditions which, in the opinion of the investigators, would jeopardize the patient or the integrity of the data obtained
- 3.1.2.12 Serious hypersensitivity reaction to egg products
- 3.1.2.13 Chronic hepatitis infection, including B and C, because of potential immune impairment
- 3.1.2.14 Clinically significant cardiomyopathy or cardiac complications, including recent myocardial infarction or cerebrovascular accident within one year, and/or unstable or uncontrolled angina
- 3.1.2.15 Previous intolerance to BCG intravesical therapy suggested by development of systemic BCG infection in the past and/or grade 4 or greater adverse effect by CTCAE v5.0.
- 3.1.2.16 Patients unable to avoid close contact or household contact with the following high-risk individuals for three weeks after the Day 1 vaccination: (a) children \leq 3 years of age, (b) pregnant or nursing women, (c) individuals with prior or concurrent extensive eczema or other eczematoid skin disorders, or (d) immunocompromised individuals, such as those with HIV.

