The CDC is the only source of the licensed vaccinia vaccine. The CDC will provide vaccinia vaccine to protect laboratory and other healthcare personnel, whose occupations place them at risk of exposure to vaccinia and other closely related orthopoxviruses, including vaccinia recombinants. The vaccine should be administered under the supervision of a physician selected by the study institution. Revaccination is recommended every 10 years. For instructions on obtaining the licensed vaccinia vaccine, contact Drug Services, National Center for Infectious Diseases, CDC at [contact].

Recombinant Vaccinia Vaccine Patient Care Implications, Contraindications and Potential Complications

Patient Care Implications and Contraindications

Cover vaccination sites with a sterile dry dressing (*e.g.*, Telfa pad). Instruct patients on proper hand-hygiene, sterile dressing care, bathing, laundering of clothing, *etc.* Treat patient bandages or dressings removed from the vaccination site as infectious waste and dispose in appropriate biohazard containers. Do not administer the recombinant vaccinia vaccine if the recipient, or for at least three weeks after vaccination, their close household contacts (close household contacts are those who share housing or have close physical contact):

- have active eczema or a history of eczema or atopic dermatitis, or Darier's disease.
- have other acute, chronic, or exfoliative skin conditions (*e.g.*, burns, impetigo, varicella zoster, severe acne, contact dermatitis, psoriasis, herpes or other open rashes or wounds), until the condition resolves.
- are pregnant or intend to become pregnant (due to the potential risk of fetal vaccinia); or are breast-feeding (due to the potential risk of contact transmission and inadvertent inoculation). It is currently unknown if vaccinia virus or antibodies are excreted in breast milk. Because there is no safety data available, patients (*i.e.*, vaccinees) should avoid becoming pregnant, fathering a child, or breast-feeding for at least 4 months following completion of therapy with the recombinant vaccine.
- are in close contact with children less than 3 years of age (due to the potential risk of contact transmission and inadvertent inoculation).
- are immunodeficient or immunocompromised (by disease or therapy), including individuals with HIV infection.

Additionally, do not administer the recombinant vaccinia vaccine if the vaccinee:

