3. **Inadvertent Inoculation:** This can occur in the vaccinee (autoinoculation) as well as in close contacts (contact transmission). Accidental infection is the most common complication of vaccinia vaccination, accounting for approximately 50% of all complications associated with vaccination and revaccination. This usually results from autoinoculation of vaccinia virus transferred from the site of the vaccination. Sites typically involved include the face, eyelids, nose, mouth, genitalia, or rectum, but can also involve the arms, legs, and trunk. Contact transmission of vaccinia, with accompanying toxicities, may occur when a recently vaccinated individual has contact with a susceptible individual. In a 1968 ten-state survey, contact transmissions were reported to occur at a rate of 27 infections per million vaccinations. The age group in which contact transmission occurred most commonly was in children \leq 5 years. Eczema vaccinatum as a result of contact transmission may result in a more severe syndrome than that seen in vaccinees, perhaps because of multiple simultaneous inoculations. About 30% of eczema vaccinatum cases reported in the 1968 ten-state survey were a result of contact transmission. It is possible that the number of cases of contact transmission would be greater in today's population, due to a largely unvaccinated patient population against smallpox. Contact transmission rarely results in postvaccinal encephalitis or progressive vaccinia. Most cases of inadvertent inoculation usually resolve without specific therapy and resolution of lesions follow the same course as the vaccination site in immunocompetent individuals. VIG can be used for severe cases involving extensive lesions or if comorbid conditions exist. VIG is contraindicated in the presence of isolated keratitis due to the risk of increased corneal scarring. VIG use can be considered in cases of ocular implantation, with keratitis, if vision-threatening or if other life-threatening vaccinia-related complications exist that require VIG therapy.

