5. **Eczema vaccinatum:** Eczema vaccinatum is a serious complication in persons with eczema and other types of chronic or exfoliative skin conditions. It can also occur among eczematous contacts of recently vaccinated persons. Vaccinia lesions (generalized papular, vesicular or pustular lesions) develop on areas of the skin that are, or had at one time been, eczematous. These areas become highly inflamed and lesions may spread to healthy skin. The rash is often accompanied by fever and individuals are systemically ill. The fatality rate for untreated cases (prior to availability of VIG) has been reported from 30-40%. Following availability of VIG, mortality was reduced to approximately 7%. Early diagnosis and prompt treatment with VIG is necessary to reduce mortality.
6. **Progressive vaccinia:** Progressive vaccinia is the most serious cutaneous complication, occurring when the local vaccination lesion fails to heal and develops progressive necrosis, with destruction of large areas of skin, subcutaneous tissue, and underlying structures. Progressive lesions may spread to other skin surfaces and to bone and viscera. Progressive vaccinia is associated with a high mortality rate. This complication has been seen in patients with a compromised immune system due to a congenital deficiency, lymphoproliferative disease, immunosuppressive treatment, or HIV infection. Management should include aggressive VIG therapy.
7. **Post-Vaccinial Encephalitis/Encephalomyelitis:** Vaccinia complications affecting the CNS are unpredictable. Post-vaccinial encephalitis typically affects children < 2 years of age and is characterized by an onset of symptoms 6-10 days following vaccination, which include seizures, hemiplegia, aphasia, and transient amnesia. Histopathological changes include generalized cerebral edema, mild lymphocytic meningeal infiltration, ganglion degenerative changes and perivascular hemorrhages. Older children and adults can

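### The contact exclusion in Section 3.1.2.16(c) is narrower than the household-contact contraindication to the vaccinia prime in Section 9.1.1, so a patient can be randomised to PANVAC and then be barred from the prime

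*Combined protocol and SAP*

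**What the plan says.** Section 3.1.2.16 applies to patients who cannot avoid close or household contact with listed high-risk people for three weeks after the first vaccination. Its skin item is "c) individuals with prior or concurrent extensive eczema or other eczematoid skin disorders". The other items are young children, pregnant or nursing women, and immunocompromised people.

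Section 9.1.1, under Patient Care Implications and Contraindications for PANVAC-V, gives a direct instruction: "Do not administer the recombinant vaccinia vaccine if the recipient, or for at least three weeks after vaccination, their close household contacts" meet any of a list of conditions. For eczema the condition is that they "have active eczema or a history of eczema or atopic dermatitis", and Darier's disease stands in the same item. A second item covers other acute, chronic or exfoliative skin conditions. Its examples begin with burns, impetigo and zoster and end with "severe acne, contact dermatitis, psoriasis, herpes or other open rashes or wounds), until the condition resolves".

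Section 3.1.2.10 has a broad skin list too, but as an exclusion on the patient's own skin. Its closing sentence gives a reason that mentions contacts: "There is an increased risk to patients or contacts with eczema, atopic dermatitis, and other immune deficiencies".

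Section 5.2.3.2 requires the prime at week 0 (+/- 7 days) for every patient in the PANVAC arm. The BCG-alone arm receives no vaccinia.

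**The concern.** Both arms are screened against Section 3.1.2.16, but only the PANVAC arm meets the bar in Section 9.1.1. A mismatch between the two lists therefore takes effect after randomisation and in one arm only. An eligible patient who lives with, say, someone with psoriasis or shingles can be allocated to PANVAC. Staff who follow Section 9.1.1 must then hold back the component that the treatment plan requires. Staff who follow the treatment plan give a live, replication-competent virus against a written contraindication, and the risk falls on a third party who is not in the trial.

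The protocol gives no reason for the word *extensive*. Its account of eczema vaccinatum in Section 9.1.1 says "It can also occur among eczematous contacts of recently vaccinated persons", and that lesions "develop on areas of the skin that are, or had at one time been, eczematous". Neither statement depends on how widespread the eczema is or was.

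**Working it through.** **Step 1. The two contact lists, item by item.**

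| Condition in an unavoidable close household contact | 3.1.2.16 | 9.1.1 |
|---|---|---|
| Extensive eczema, current or past | excluded | barred |
| Limited eczema, current or past | not excluded on the plain reading of *extensive* | barred |
| Atopic or contact dermatitis | arguably excluded as eczematoid | barred (contact dermatitis until resolved) |
| Darier's disease | not mentioned | barred |
| Burns, impetigo, zoster, severe acne, psoriasis, herpes, open rashes or wounds | not mentioned | barred until resolved |
| Pregnant or nursing; immunocompromised | excluded | barred |
| Intends to become pregnant | not mentioned | barred |
| Young children | 3 years or younger | under 3 years |

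The skin rows carry the point. The gap is certain for Darier's disease and the non-eczematoid conditions. For limited eczema it depends on one word.

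**Step 2. Does another clause close the gap?** Section 3.1.2.10 excludes on the patient's skin; its mention of contacts is rationale, not a criterion. Section 3.1.2.11 concerns medical conditions that endanger the patient or the data. Section 3.1.2.7 lists social situations that limit compliance, which is discretionary and does not name contacts. Section 5.3.3 asks for a review of safe-handling precautions before dosing, which comes after randomisation. None closes it.

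**Step 3. Expected harm to contacts.** Section 9.1.1 cites a 1968 survey in which "contact transmissions were reported to occur at a rate of 27 infections per million vaccinations". With equal allocation of 49 to 54 patients, 24.5 to 27 receive the prime.

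- Contact infections: 27/1,000,000 x 24.5 = 0.00066, and x 27 = 0.00073, so about 0.0007.
- Eczema vaccinatum in a contact: the adult vaccinee rates are 4.5 (revaccination) and 30.3 (primary) per million, and about 30% of cases arose by contact. *Assuming* that share applies to these adult rates, the contact rate is the vaccinee rate x 0.3/0.7, which is 1.9 and 13.0 per million. Times 24.5 and 27 patients respectively, that is 0.00005 to 0.00035 expected cases.

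These are survey averages. Subcutaneous dosing and a covered site should lower them; an eczematous contact who cannot be avoided raises them.

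**Step 4. Power, for illustration only.** Inputs are from Section 14.1: exponential recurrence-free survival; 1-year rates of 37.5%, 20% and 48% on BCG and 65%, 44.7% and 65% on the combination; subgroup mix 1:5:1; accrual of 1 per month for 6 months, then 2 per month; 12 months of further follow-up; one-sided 15% log-rank test.

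- The plan's figures: 84% power, 40 events, 28 months of accrual at N = 49. Simulation gives 84.7%, 39.6 events and 6 + 43/2 = 27.5 months, so the plan's figures are reproduced closely.
- The documents do not say how many patients are affected. *Assume* one PANVAC patient loses half or all of the log hazard ratio. Power at N = 49 becomes 83.7% or 82.8%, a loss of 1.0 or 1.9 points. At the ceiling of 54 it goes from 87.4% to 86.5% or 85.8%.

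**The case against.** The strongest reply is that the mismatch has little practical effect.

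- **The eczema part is ambiguous.** *Extensive* may modify only the word eczema, leaving other eczematoid disorders without an extent limit, and the rationale in 3.1.2.10 points towards the wider reading. This stands in part. A reader might infer that every contact with mild or past eczema passes screening, but the wording does not settle that. It does not help with Darier's disease, psoriasis, zoster, herpes, burns or wounds.
- **A rule for a delayed prime exists.** A reader might infer that the protocol is silent on a prime deferred for a contact's condition, or that this mismatch itself erodes the planned 21 days between prime and BCG, for which Section 12.1.1.2 gives a safety reason. Section 6.2.1 has a general rule: a delay not due to toxicity may run to 42 days, and BCG is not affected. Any shortening of the gap follows from that rule, and the windows of +/- 7 days for the prime and +/- 2 days for BCG already allow some. This objection stands.
- **Keeping such patients in the analysis is right.** Section 14.4.2 bases conclusions on all eligible patients. That protects the comparison, and any dilution is conservative. This stands too.
- **Only unavoidable contacts matter.** That is true, but 3.1.2.16 asks about avoidance only for the contacts it lists, so nobody is prompted to ask about the omitted conditions.
- **The Appendix C patient sheet and the eligibility checklist were not available to read.** The sheet may advise on contacts, but advice to patients would not change eligibility.

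**Conclusion.** The point holds as a conflict between two sections. Followed as written, the plan can randomise a patient whom its own contraindication then bars from the prime, in one arm only. This is certain for Darier's disease and for non-eczematoid skin conditions, and holds for limited eczema on the plain reading of *extensive*.

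Its size is modest. The documents give no count of affected households. Many of the omitted conditions are temporary, so delay is the likelier result for those; a contact's history of eczema is permanent.

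Two stronger conclusions might be inferred, and the documents support neither. One is that contacts face a material risk: the expected numbers in Step 3 are far below one. The protocol also reports no eczema vaccinatum among 450,293 military vaccinees, though it cautions that those data are not directly comparable. What remains is severity if a case occurs: Section 9.1.1 gives mortality of about 7% with vaccinia immune globulin available and 30-40% untreated. The other is that the trial loses power. The losses in Step 4 follow only from an assumed affected patient with an assumed loss of benefit. A delayed prime may cost nothing, and a missed one still leaves four fowlpox boosts.

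The case for a change rests on internal consistency, the third-party contraindication and the low cost of the remedy.

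**What to change.** Keep the lead-in of 3.1.2.16 about contacts who cannot be avoided for three weeks, and replace (c) with: *individuals with active or past eczema or atopic dermatitis, Darier's disease, other eczematoid skin disorders, or any other acute, chronic or exfoliative skin condition until it resolves*. Check it before randomisation in both arms. When a contact's condition is expected to resolve, defer randomisation, not the prime. No new line in Section 6.2.1 is needed for this point.

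The cost is one reworded criterion, one checklist line, and a small, unknown number of candidates excluded or deferred in both arms. Some would be lost for good, because a contact's chronic condition such as psoriasis may not resolve. If an assumed 2%, 5% or 10% of candidates were excluded, accrual of 49 would take 27.5/0.98, 27.5/0.95 or 27.5/0.90 months, which is 0.6, 1.4 or 3.1 months longer. Screening will not catch a contact's condition that arises after randomisation; the existing delay rule in Section 6.2.1 would apply there.

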3.1.3 Inclusion of Women and Minorities

Both men and women of all races and ethnic groups are eligible for this trial.

3.2 RECRUITMENT STRATEGIES

This study will be listed on available websites (www.clinicaltrials.gov and others) and participants will be recruited from the current patient population at NIH.

3.3 SCREENING EVALUATION

- 3.3.1 Clinical Evaluation (within 28 days of before starting treatment).
 - 3.3.1.1 History and physical examination
 - 3.3.1.2 ECOG performance status
- 3.3.2 Viral Studies and Prior Vaccination Status
 - 3.3.2.1 HIV test within 8 weeks of initial visit and repeat if clinically indicated
 - 3.3.2.2 Hepatitis B and C titers within 8 weeks of initial visit and repeat if clinically indicated
 - 3.3.2.3 Document known prior vaccinia vaccination (small pox vaccine)

3.4 BASELINE EVALUATION

- 3.4.1 Laboratory studies (within 28 days before starting treatment)
 - 3.4.1.1 Complete blood count plus differential and platelet count
 - 3.4.1.2 Serum chemistries (Na+, K+, Cl-, CO2, glucose, BUN, creatinine, albumin, calcium, magnesium, phosphorus, alkaline phosphatase, ALT, AST, total bilirubin, LDH, pre-albumin) with BUN and creatinine
 - 3.4.1.3 PT, PTT
 - 3.4.1.4 6 green top tubes of blood will be drawn for PBMCs, HLA Typing, and sera for correlative/exploratory research aims (e.g. ELISPOT, CD4+ Antigen-specific responses, etc.) on day 1 of study enrollment
 - 3.4.1.5 Beta-HCG for women of child-bearing age (within 48 hours prior to day 1). In addition, patients, both male and female, should be willing to practice effective birth control during the study and four months following the last study treatment, unless they have had a prior hysterectomy, bilateral oophorectomy, or vasectomy
- 3.4.2 Urine studies
 - 3.4.2.1 Urinalysis with urine culture (prior to operative procedures and within 2-21 days of operative procedures)
 - 3.4.2.2 Urine cytology (prior to operative procedures and within 2-21 days of operative procedures or at time of operative procedure)
 - 3.4.2.3 Urine collection for correlative/exploratory research aims (e.g. inflammatory cells, cytokines) at the time of operative procedure
- 3.4.3 Imaging (within past 45 days and of adequate quality)
 - 3.4.3.1 Chest X-ray
 - 3.4.3.2 Computerized Tomography (CT) urogram or Magnetic Resonance Imaging (MRI) urogram. If urogram protocol not available or contrast allergy/poor renal function preclude such imaging, then CT or MRI of the abdomen/pelvis will suffice
- 3.4.4 Pathology

3.4.4.1 Formal review of available previous bladder tumor specimens by the Laboratory of Pathology, NCI, to confirm the bladder cancer diagnosis prior to enrollment into the study. For patients enrolled at collaborating trial sites, diagnosis must be confirmed by the Department of Pathology at the institution where the patient is enrolled on the trial. Pathology can also be reviewed by the Laboratory of Pathology at the NCI if the participating trial site prefers another pathologic evaluation.

3.4.4.2 Tissues obtained at the NCI will be used to confirm diagnosis and for study of immune-related markers. With preoperative patient permission, extra tissue not sent to Laboratory of Pathology, NCI, will be frozen for future analysis of immune-related markers and tumor infiltrates. This additional harvested tissue will be used for research purposes only and is not required for a candidate to participate in this protocol. Tissue will also be collected at collaborating trial sites as specified by Appendix E (Section **17.5**).

3.5 ACCRUAL ESTIMATES

Accrual Targets					
Ethnic Category	Sex				
	Females		Males		Total
Hispanic or Latino	4	+	4	=	8
Not Hispanic or Latino	23	+	23	=	46
Ethnic Category: Total of all subjects	27	+	27	=	54
Racial Category					
American Indian or Alaskan Native	1	+	1	=	2
Asian	1	+	1	=	2
Black or African American	4	+	4	=	8
Native Hawaiian or other Pacific Islander	1	+	1	=	2
White	20	+	20	=	40
Racial Category: Total of all subjects	27	+	27	=	54

Accrual Rate: 2-3 patients/month

Total Expected accrual: Min: 49 Max: 54

Projected Start Date of study: December 1, 2013

Anticipated Primary Completion Date: December 1, 2017

